8.4 Serious Adverse Events

An adverse event or adverse reaction is considered serious if, in the view of either the Investigator or Sponsor, it results in any of the following outcomes:

- Death,
- A life-threatening adverse event,
 - NOTE: An adverse event or adverse reaction is considered “life-threatening” if, in view of either the Investigator or Sponsor, its occurrence places the subject at immediate risk of death. It does not include an event that, had it occurred in a more severe form, might have caused death.
- Requires hospitalization or prolongation of existing hospitalizations,
 - NOTE: Any hospital admission with at least one overnight stay will be considered an inpatient hospitalization. An emergency room visit without hospital admission will not be recorded as a serious adverse event (SAE) under this criterion, nor will hospitalization for a procedure scheduled or planned before signing of informed consent. However, unexpected

complications and/or prolongation of hospitalization that occur during elective surgery should be recorded as adverse events and assessed for seriousness. Admission to the hospital for social or situational reasons (i.e., no place to stay, live too far away to come for hospital visits) will not be considered inpatient hospitalizations.

- A persistent or significant disability/incapacity or substantial disruption of the ability to conduct normal life functions,
- A congenital anomaly or birth defect,
- An important medical event.
 - NOTE: Important medical events that may not result in death, be life-threatening, or require hospitalization may be considered an SAE when, based upon appropriate medical judgment, they may jeopardize the subject and may require medical or surgical intervention to prevent one of the outcomes listed above. Examples of such medical events include allergic bronchospasm requiring intensive treatment in an emergency room or at home, blood dyscrasia or convulsions that do not result in inpatient hospitalizations, or the development of drug dependency.

8.5 Serious Adverse Event Reporting – Procedures for Investigators

Initial Reports

Serious adverse events will be reported in compliance with country-specific regulatory requirements relating to safety reporting to the regulatory authority IRB/EC and investigators.

All SAEs occurring from randomization until 28 days following the last administration of study drug must be reported to the Contact Research Organization (CRO) Clinical Safety within 24 hours of the knowledge of the occurrence (this refers to any adverse event that meets any of the aforementioned serious criteria). All SAEs that the Investigator considers related to study drug occurring after the 28-day follow-up period must be reported to the Aridis Pharmaceuticals Inc.

To report the SAE, complete the SAE form electronically in the EDC system for the study. When the form is completed, CRO Safety personnel will be notified electronically and will retrieve the form. If the event meets serious criteria and it is not possible to access the EDC system, send an email to CRO Safety at [contact] or call the CRO SAE hotline (phone number listed below), and fax/email the completed paper SAE form to CRO (fax number listed below) within 24 hours of awareness. When the EDC system becomes available, the SAE information must be entered within 24 hours of the system becoming available.

Safety Contact Information: Clinical Safety

SAE hotline – USA:

[contact], dial 3 or [contact], dial 3

[contact] or [contact]

Email: [contact]

SAE hotline – Europe:

[contact]

[contact]

Email: [contact]

Follow-Up Reports

The Investigator must continue to follow the subject until the SAE has subsided or until the condition becomes chronic in nature, stabilizes (in the case of persistent impairment), or the subject dies.

Within 24 hours of receipt of follow-up information, the Investigator must update the SAE form electronically in the EDC system for the study and submit any supporting documentation (e.g., subject discharge summary or autopsy reports) to Clinical Safety via fax or e-mail. If it is not possible to access the EDC system, refer to the procedures outlined above for initial reporting of SAEs.

8.6 Pregnancy Reporting

If a study subject becomes pregnant during the study or within 28 days of discontinuing study drug, the Investigator should report the pregnancy to Clinical Safety within 24 hours of being notified. Clinical Safety will then forward the Exposure in Utero form to the Investigator for completion.

A subject becoming pregnant while on study drug will immediately be withdrawn from the study and early termination study procedures will be performed.

The subject should be followed by the Investigator until completion of the pregnancy. If the pregnancy ends for any reason before the anticipated date, the Investigator should notify Clinical Safety. At the completion of the pregnancy, the Investigator will document the outcome of the pregnancy. If the outcome of the pregnancy meets the criteria for immediate classification as an SAE (i.e., postpartum complication, spontaneous abortion, stillbirth, neonatal death, or congenital anomaly), the Investigator should follow the procedures for reporting an SAE.

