Study subjects will receive a single treatment dose (at Day 0) in addition to SOC antibiotic treatment, and then enter a safety, efficacy and PK follow-up study period for a total study duration of 28 days. The selection of SOC antibiotics is made in accordance with local best practices at the discretion of the investigator and should not exceed the duration of 14 days.

The clinical course of pneumonia will be assessed daily by the investigator. Once Clinical Cure has been determined, the clinical status of the subject will be monitored to confirm continuation of Clinical Cure, re-infection (pneumonia due to *P. aeruginosa*), or new infection (pneumonia due to an unknown pathogen or a pathogen other than *P. aeruginosa*). "Clinical Cure" will be declared at any time during the study by the PI, provided that the required criteria are met either based on documented improvements in signs and symptoms, +/- changes documented by chest X-ray (if performed as part of SOC), as interpreted by the investigator.

The assessment of Clinical Cure (resolution of pneumonia) by the site investigator will be used for the primary analysis. An adjudication committee will apply newly defined Clinical Cure criteria post hoc in a secondary analysis. “Clinical Cure” will be assessed for analytical purposes on Day 7, 14, 21 (primary efficacy endpoint) and 28.

Clinical safety assessments will be performed on an ongoing basis while predefined laboratory assessments will be performed at baseline, and thereafter at Day 4, 7, 14, 21, and 28. Test results obtained for medical reasons between these mandatory time points will be assessed for adverse events and documented accordingly.

Secondary efficacy endpoints will be assessed in a similar manner during the 28-day period when appropriate, daily when possible, (e.g., Time on mechanical ventilation including if tracheostomy is in place; Time on supplemental oxygenation; measures of respiratory health such as changes in PaO₂/FiO₂ using arterial blood gases and/or pulse oximetry measurements), or upon occurrence (e.g., antibiotic utilization, duration of stay in the ICU, duration of hospitalization, duration of intubation with ventilation, or duration of mechanical ventilation if tracheostomy in place).

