10. Any sexually active subjects who is unwilling to use acceptable methods of contraception for 120 days after dosing. WOCBP must agree to use to an effective method of birth control (e.g., prescription oral contraceptives, contraceptive injections, contraceptive patch, intrauterine device, barrier methods, abstinence) or male partner sterilization alone for the duration of the study and for at least 120 days after dosing. Males with female partners of reproductive potential must agree to practice abstinence or to use a condom (male) plus an additional barrier method (female partner) of contraception for the duration of the study and for at least 120 days after dosing.
11. Known lack of treatment compliance from prior studies or ongoing medical care based on medical records and PI's judgment and/or the capacity of the patient to comply with all study requirements.
12. Any medical, psychological, cognitive, social or legal conditions that would interfere in the ability to give an Informed Consent OR the absence of a legally valid representative of the patient or independent physician allowed and able to give consent on his/her behalf.
13. Participation as subject in another interventional study within 30 days prior to the first dose of study treatment, or planned participation in such a study during the study or within 30 days of its completion by the patient. Patients who participate in observational or epidemiological studies are also eligible provided this does not interfere with their capacity or the capacity of the study staff to comply with all study requirements.

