5.5.4 Treatment Compliance

The study drug will be administered once, intravenously, in a strictly monitored setting. Compliance will be recorded by confirming the start and stop dates and times of the infusion to show that the study drug was administered per the amount indicated by the EDC / IWRS system.

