8.2 Contraceptive Requirements and Pregnancy Testing

Females of child bearing potential must agree to use at least 2 effective methods of birth control (e.g., prescription oral contraceptives, contraceptive injections, contraceptive patch, intrauterine device, barrier methods, abstinence) or male partner sterilization alone for the duration of the study and for at least 120 days after dosing. Males with female partners of reproductive potential must agree to practice abstinence or to use a condom (male) plus an additional barrier method (female partner) of contraception for the duration of the study and for at least 120 days after dosing.

WOCBP must have a negative pregnancy test result at Screening (serum or urine) to meet the eligibility criteria for enrollment. Women who are post-menopausal as evidenced by the absence of menstruation for at least 1 year prior to Screening Visit are eligible; the date of the last menstruation is to be recorded in the study file unless postmenopausal status is obvious due to age.

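### Pregnancy reporting stops at about Day 28 after the single dose, while contraception is required to at least Day 120, so pregnancies beginning in the 92 days between are not covered.

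*Protocol*

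**What the plan says.** Section 8.6 defines the pregnancies it covers by when they begin: "If a study subject becomes pregnant during the study or within 28 days of discontinuing study drug". For those, the investigator has 24 hours from learning of the pregnancy to notify Clinical Safety and then completes an in-utero exposure form. Follow-up is long: "The subject should be followed by the Investigator until completion of the pregnancy".

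Three other parts of the protocol fix the calendar:

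- Section 5.5.4: "The study drug will be administered once, intravenously, in a strictly monitored setting". Section 3.1 places that dose on Day 0.
- Section 3.1: after dosing, subjects enter a "follow-up study period for a total study duration of 28 days".
- Section 8.2 requires contraception "for the duration of the study and for at least 120 days after dosing". It applies to women of child-bearing potential and to men with female partners of reproductive potential. Exclusion criterion 10 in Section 4.2 sets the same 120 days.

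Two safety rules bear on later events. Section 8.4 lists "A congenital anomaly or birth defect" among the outcomes that make an event serious. Section 8.5 says: "All SAEs that the Investigator considers related to study drug occurring after the 28-day follow-up period must be reported". The SAP sets no rule on pregnancy reporting.

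**The concern.** With one dose on Day 0, counting 28 days from discontinuation adds nothing to a study that itself lasts 28 days. The wording suits a drug given repeatedly better than a single infusion of a long-lived antibody. The sponsor asks for precautions until at least Day 120, yet the protocol does not ask to hear of a pregnancy that begins after about Day 28.

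The covered period is also probably the less informative one. Subjects enter ventilated in an ICU, and many will spend much of the first 28 days in hospital. Conception is more plausible after discharge. This is an inference; the documents give no data on it.

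What is at stake is safety information. If contraception fails while precautions are still required and some drug is expected to remain, the sponsor may receive no exposure or outcome record unless an SAE judged related occurs. No efficacy result is touched.

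**Working it through.** **Inputs**

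- Dose: one, on Day 0 (Protocol 3.1, 5.5.4).
- Study duration: 28 days (3.1).
- Final-visit tolerance: ±2 days (Table 6-1, note 17).
- Exit call for subjects who stop assessments early: Day 28, up to 7 days later (8.8).
- Pregnancy rule: during the study, or 28 days from discontinuation (8.6).
- Contraception: at least 120 days after dosing (4.2, 8.2).
- Half-life: about 3 weeks for this product (1.2); 3 to 4 weeks for an IgG1 in general (1.1).

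**End of the reporting window.** The discontinuation limit ends at Day 0 + 28 = Day 28, which reproduces the protocol's own 28 days. The study limit also ends at Day 28. It moves to 28 + 2 = Day 30 with the visit tolerance, or 28 + 7 = Day 35 if the latest exit call counts as study time.

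**Uncovered days** = 120 − end of window:

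| Window ends | Uncovered | Days | Share of 120 |
|---|---|---|---|
| Day 28 | Day 29 to 120 | 120 − 28 = 92 | 77% |
| Day 30 | Day 31 to 120 | 120 − 30 = 90 | 75% |
| Day 35 | Day 36 to 120 | 120 − 35 = 85 | 71% |

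The shares are of calendar days, not of pregnancies or of risk. The documents give no number of women of child-bearing potential. Because the test is when the pregnancy begins, one that starts by Day 28 but is discovered later is still covered.

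**Drug remaining, as illustration only.** Assume one-phase decay, with fraction remaining = 0.5^(t / half-life):

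- Day 28: 0.5^(28/21) = 0.397; 0.5^(28/28) = 0.500.
- Day 120: 0.5^(120/21) = 0.019; 0.5^(120/28) = 0.051.

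About 40% to 50% would remain at Day 28 and about 2% to 5% at Day 120. The lower figure in each pair uses the product's stated half-life; the upper uses the top of the general IgG1 range. Half-life in these patients may differ: Section 5.2 says bacterial load may affect the PK profile, and Section 9.3.3 treats similarity to healthy volunteers as a hypothesis to be assessed. The gap does not depend on this calculation.

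**What the other rules catch after Day 28.**

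- A congenital anomaly, a death, a hospitalization or an important medical event meets a seriousness criterion in Section 8.4. Under Section 8.5 it must be reported after the 28-day period only if judged related.
- Spontaneous abortion, stillbirth, neonatal death and postpartum complication are named as SAE outcomes only in Section 8.6, for pregnancies already followed there.
- An uncomplicated pregnancy is not listed as an SAE, so no late rule reaches it.
- Sections 8.5 and 8.7 defer to country-specific safety requirements, which may add duties but are not set out.

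**The case against.** The strongest reply is that nothing is inconsistent. Contraception is a precaution and pregnancy reporting is data collection; no rule in the protocol says their windows must match. The 28 days also agree with the collection period for adverse events (8.3) and SAEs (8.5). This is right as far as it goes: the two windows do not contradict each other, and the shorter one is a design choice. But agreement with the AE window does not make 28 days a good fit for a drug with a half-life of about 3 weeks and a 120-day precaution period.

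A second reply is that the late-SAE rule catches more than it seems to. Section 8.3.3 allows an event to be called unrelated only if its timing rules out a causal link and another cause is suspected. Section 8.3.1 treats a link that cannot be ruled out as a reaction. If drug persists, a serious pregnancy outcome would not easily meet the unrelated category. That has force, and it narrows the gap chiefly to uncomplicated pregnancies. It does not close it. Section 8.3.3 also reserves the related category for events with no other identifiable cause, so a late miscarriage with an alternative explanation could go unreported.

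Third, the consent pages were removed from the documents reviewed and may tell subjects to report later pregnancies. That is unknown. It limits certainty about what would be lost in practice, but not about what Section 8.6 requires.

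Finally, the benefit is small and later capture would be passive. Both points stand, and they are why the weight is low.

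**Conclusion.** The concern holds as a minor point. Pregnancies that begin from Day 29 to Day 120, 92 calendar days, fall outside Section 8.6 although contraception is still required; the figure is 85 days on the most generous reading of when the study ends. This rests only on the protocol's day counts and is certain on the text. How much information would be lost is less certain: it depends on the consent form, on country rules, on how relatedness is judged and on how many pregnancies occur. Few are expected among about 154 ventilated ICU patients, and the documents show no signal of fetal risk. Neither the primary analysis nor any other efficacy analysis is affected.

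**What to change.** In Section 8.6, replace the limit of 28 days from discontinuation with 120 days after dosing. At the last study contact, tell the subject or representative to report any pregnancy that begins in that period. Add no visits or calls. The uncovered interval then falls from 92 days to 0.

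This covers study subjects only. Men with female partners are bound by the same 120 days, so the sponsor may also consider including partner pregnancies, with follow-up only if the partner agrees. That is optional and separate from the point above.

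The cost is one protocol amendment, which under Section 12.1 needs the same review and approval as the original protocol, across approximately 120 sites. A consent-form change would probably follow, and Section 11.3 requires sponsor and IRB/EC agreement before its use. Bundling both with the next amendment keeps the burden small. With no contact scheduled after Day 28 (+7 days), reporting would depend on subjects coming forward and may be incomplete.

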8.7 Expedited Reporting

The Sponsor, or CRO (on behalf of the Sponsor), will report all relevant information about initial suspected unexpected serious adverse reactions (SUSAR) that are fatal or life-threatening as soon as possible to the FDA, applicable competent authorities in all the Member States concerned, and to the Central Ethics Committees, and in any case no later than 7 days after knowledge by the Sponsor or CRO of such a case, and relevant follow-up information will subsequently be communicated within an additional 8 days.

All other SUSARs will be reported to the FDA, applicable competent authorities concerned and to the Central Ethics Committees concerned as soon as possible but within a maximum of 15 days of first knowledge by the Sponsor or CRO.

The Sponsor and the CRO (on behalf of the Sponsor) will comply with country-specific regulatory requirements relating to safety reporting to the regulatory authority, IRB/EC and investigators if country requirements are different than the above.

The Sponsor will also inform all investigators as required.

Expedited reporting of suspected unexpected serious adverse reactions related to non-investigational medical products (NIMPs) will not be necessary. Listings of cases related to NIMPs will be included in the Development Safety Update Report.

8.8 Follow-up Phone Calls

For subjects who decide to discontinue assessments prior to Day 28, a study exit safety follow-up phone call will be conducted on Day 28 (+7 days) to assess survival, Clinical Cure, and adverse events.

For subjects deemed clinically cured and discharged from the hospital, subjects are encouraged to return to the clinic to receive study procedures for the remaining key visit days until Day 28. If not able to visit the clinic on key visit days, a follow-up phone call will be conducted on key visit days (Day 4, 7, 14, 21 and 28) until Day 28.

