
 1. To be performed if medically necessary. Follow-up airway specimens to be obtained as medically necessary and prior to extubation and at Day 28 (if not extubated prior to then) for quantitative or semi-quantitative culture. 2. SOFA and respiratory data to be collected on Day 0, 12 hours after treatment initiation and on Day 4, 7, 14, 21, 28 while intubated and mechanically ventilated. Parameters for SOFA score calculation should not be older than 72 hours. 3. ADA only at screening / baseline and Day 28, or at early termination. 4. Pre-dose PK sample to be obtained prior to treatment initiation. 5. PK samples to be obtained for the FULL PK sub-study at the following times after initiation of treatment: 2 hours (end of infusion), 4h, 12h, and 24 hours and 1 sample at each of the following visits: Day 4, 7, 14, 21, and 28. 6. PK samples for the SPARSE PK sub-study at the following times after initiation of treatment: 1 sample at 2 hours (end of infusion), 1 sample at either 4h, 12h, or 24 hours post-treatment initiation (inclusive) and 1 sample at any of the following visits: Day 4, 7, 14, 21, or 28. 7. Eligible subjects are randomized on Day -1, Treatment day is Day 0 for the purpose of monitoring and collecting the required samples over the first 24 hours. 8. Clinical Cure will be assessed at Day 7, 14, 21, 28 for the analytical purposes. 9. Discharge data to be obtained when discharge occurs or Day 28, whichever occurs first. 10. Patients with pneumonia who are intubated are eligible for screening regardless of the type of pneumonia, which will be recorded at the time of screening for all study subjects. 11. Vital signs will be recorded at baseline prior to treatment (time 0) and then at 1, 2, 4, 12, and 24 hours post treatment. Vital signs will also be recorded daily thereafter. 12. In addition to the screening timepoint, chest x-ray(s) are to be taken at any time as medically indicated. 13. Women of child bearing potential must take a urine or serum pregnancy test at the time of Screening. 14. For subjects with early discharge, effort must be made to perform all protocol defined procedures outlined for End of Study/Early Termination. 15. Subjects who decide to discontinue study assessments prior to Day 28 will receive a study exit safety follow-up phone call on key days (Day 4, 7, 14, 21, 28) until Day 28 (+7 days) to assess Clinical Cure, survival and the status of any adverse events. 16. Changes in PaO₂/FiO₂ ratio (e.g. by arterial blood gases), if available and whenever possible OR changes in non-invasive measures of oxygenation (e.g. by pulse oximetry) 17. A few days before or after the specified date is acceptable (± 2 days) 					

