7 EFFICACY ASSESSMENTS

7.1 Primary Clinical Efficacy Parameter

The proportion of patients with Clinical Cure at Day 21 in patients treated with Aerucin® versus the placebo group as assessed by the investigator. The investigators' assessment will be the primary analysis of the primary endpoint.

Additionally, newly defined Clinical Cure (**Table 7-1**) and will be applied post-hoc by an independent adjudication committee.

Table 7-1 Criteria for Clinical Cure

1. The subject must be alive through the index day visit
--

2. The patient must have improved respiratory function evaluated at the index day, because: 
• The patient is now off the ventilator and extubated or
3. if the patient entered the study with mechanical ventilation due to reasons other than pneumonia and was assessed " likely ventilated beyond day 28 " at screening, criteria #1 (survival) and #3 (no signs and symptoms of pneumonia) are sufficient to establish Clinical Cure (presumed not ventilated)

4. The subject must show no clinical signs and symptoms of bacterial pneumonia at the index day, which is determined by 
• Not receiving any antibiotic therapy active against the initial P. aeruginosa strain or against persisting pulmonary bacterial infection for 48 hours (antibiotic therapy for documented extra-pulmonary infection permitted) 
and
 • Resolution of signs and symptoms of bacterial pneumonia, as determined by the PI based on their clinical assessment. Parameters to be considered may include:
○ Fever > 38°C or hypothermia (< 35°C) attributable to the primary bacterial pneumonia○ Tachypnea or shortness of breath (> 22 respirations/min) if off the ventilator and/or back to baseline respiratory rate○ Tachycardia (> 100 bpm) or bradycardia (< 60 bpm) and/or back to baseline heart rate○ Improvement of hypoxemia (ABG or PaO₂/FiO₂ > 200 or pulse oximetry > 90%)○ If patient still produces sputum - negative P. aeruginosa culture from sputum, blood or pleural fluid
--

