## 6.4. Efficacy Analyses

### 6.4.1. Primary Clinical Efficacy Endpoint

#### 6.4.1.1. Primary Analysis

The primary efficacy endpoint is the **proportion of patients** with clinical cure at Day 21 in patients treated with Aerucin® versus the placebo group as assessed by the investigator. The investigators' assessment will be the primary analysis of the primary endpoint.

The proportion of patients with clinical cure rate at Day 21 will be summarized by randomized treatment based on the micro-ITT Population and will be analyzed using a **stratified Cochran-Mantel-Haenszel (CMH) test** based on baseline randomization strata (stratum 1: VABP or non-VABP, stratum 2: PaO2/FiO2 ≤200 or >200, and stratum 3: Americas, Eastern EU, Western EU and Asia). The **P-value** from the stratified CMH test will be presented. Prior to the unblinding, the assessment of each strata and strata combinations with respect to the sample size and the corresponding number of endpoints if any or some strata need to be combined to be able to process with the analysis or an **alternative method is called for (e.g. Fisher's Exact test).**

For the primary analysis, subjects who dropped out or had missing outcome data will be included in the denominator. Missing data will be imputed using the nearest clinical data available prior to that day, i.e. LOCF approach.

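### Protocol Section 8.8 and Table 6-1 footnote 15 give different call schedules for subjects who stop assessments, and only the footnote includes a Day 21 contact

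*Protocol*

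**What the plan says.** Protocol Section 8.8, first paragraph, covers one group, introduced as "For subjects who decide to discontinue assessments prior to Day 28". For them it plans one contact: "a study exit safety follow-up phone call will be conducted on Day 28 (+7 days) to assess survival, Clinical Cure, and adverse events".

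Footnote 15 of the schedule of assessments (Protocol Table 6-1) covers the same group, and the SAP repeats it under its Table 1. It provides a "phone call on key days (Day 4, 7, 14, 21, 28) until Day 28 (+7 days) to assess Clinical Cure, survival" and the status of adverse events.

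The second paragraph of 8.8 does mention calls on the key days, but for other subjects: "For subjects deemed clinically cured and discharged from the hospital, subjects are encouraged to return to the clinic". Those who cannot attend are telephoned instead.

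The primary endpoint in Protocol Section 7.1 is "The proportion of patients with Clinical Cure at Day 21 in patients treated with Aerucin® versus the placebo group as assessed by the investigator". For a Day 21 outcome that is not available, SAP Section 6.4.1.1 states: "Missing data will be imputed using the nearest clinical data available prior to that day". Subjects who dropped out stay in the denominator.

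**The concern.** The two instructions concern the same subjects and the same exit call but name different days. Only one of them includes the day of the primary endpoint. Both list Clinical Cure among the things the call assesses, so a call that is not made is an outcome assessment that is not made.

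A site that reads only the section on follow-up calls would conclude that key-day calls are for cured, discharged subjects and that those who stop assessments get one call at the end. It would comply with 8.8 and breach the schedule table. The protocol foresees approximately 120 sites, many with only a few patients, so practice could differ from site to site. At stake are Day 21 outcomes that could have been collected and are instead filled from an earlier date.

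**Working it through.** The main check compares texts; the arithmetic only bounds the size.

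**1. Same subjects, same call.** Both texts address subjects who choose to stop assessments before Day 28. Both describe a study-exit safety call and name Clinical Cure, survival and adverse events. They differ only in the days: Day 28 (+7) in 8.8; Days 4, 7, 14, 21 and 28 in footnote 15.

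**2. Other sources of a Day 21 status.**
- The second paragraph of 8.8 is limited to subjects who are cured and discharged.
- Protocol Section 6.6 requires a Day 21 assessment inside or outside the ICU, but these subjects have stopped assessments.
- Protocol Section 4.3 requires End of Study data at premature withdrawal, and Section 6.7 includes a full assessment of the pneumonia in that visit. This gives the status on the withdrawal day, not on Day 21.

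**3. Whether the late call can stand in.** SAP Sections 6.1.5 and 6.4.1.1 fill a missing Day 21 outcome only from data before Day 21. A call between Day 28 and Day 35 (28 + 7) is therefore not used. The sensitivity analyses in SAP Section 6.4.1.1 do not recover the status either: one carries a failure forward and otherwise assigns an indeterminate outcome, one uses observed cases, and one uses the per-protocol set, which requires study completion.

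**4. Who is exposed under 8.8, by time of stopping.**
- Before Day 7: no contact for Day 7, Day 14 or Day 21 cure.
- From Day 7 to before Day 14: no contact for Day 14 or Day 21 cure.
- From Day 14 to before Day 21: no contact for Day 21 cure.
- From Day 21 to before Day 28: Day 21 falls before the stop, so its required assessment is already due; no loss from 8.8.

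Day 28 cure has a call under both schedules.

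**5. Size.** Inputs from Protocol Section 9.2: 69 subjects per group needed, 10% drop-out, cure rates of 65% and 85%.
- The plan's inflation step reproduces: 69 / (1 − 0.10) = 76.7, rounded up to 77 per arm; 2 × 77 = 154.
- Number affected per arm = 77 × 0.10 × s × r × f, where s is the share of drop-outs who stop before Day 21, r the share of those who are alive and reachable, and f the share of those at sites following 8.8. The documents give none of these three, so each can lie anywhere from 0 to 1.
- Ceiling, with s = r = f = 1: 77 × 0.10 = 7.7, about 8 per arm. The range is 0 to 7.7.
- Weight of one subject: 1 / 77 = 1.3 percentage points of the arm's cure rate.
- Ceiling weight: 8 / 77 = 10.4, about 10 points, set against an assumed difference of 85 − 65 = 20 points.

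**The case against.** The strongest reply is that the exposed group is narrow and its outcomes are not left blank. Leaving the ICU after improvement is not withdrawal, and cure data are still to be collected through Day 28 (Protocol Section 4.3). Cured, discharged subjects have key-day calls within 8.8 itself. The value carried forward would often be a documented investigator assessment made at withdrawal. The schedule table, in both documents, shows that key-day contact was intended. All of this stands, and it limits the size of the problem without removing the contradiction.

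Four stronger readings are tempting, and the documents do not support them:

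- *Everyone who stops assessments loses the primary outcome.* Subjects who stop on or after Day 21 should already have their Day 21 assessment.
- *About 8 per arm is the expected loss.* That figure treats every drop-out as stopping before Day 21, alive, reachable and at a site following 8.8. Section 4.3 lists withdrawn consent and loss to follow-up among the reasons for leaving, and Section 6.7 names death as a possible reason for early termination. Some of these subjects would yield no Day 21 call under either schedule.
- *The 10 points are a bias.* They are the share of an arm's rate that would rest on carried-forward values. An error of that size would need every such value to be wrong in the same direction. An uncured subject may later be cured and a cured one re-infected, so errors can go both ways.
- *Survival at Day 21 is lost as well.* A subject alive at the Day 28 call was alive at Day 21, and for a death the date can be asked. What cannot be used from that call is Day 21 cure status.

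It may also be said that the SAP already uses a Day 21 call result, since carry-forward applies only to missing data. That is a fair reading, but the SAP does not say so in terms, and stating it costs one sentence.

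**Conclusion.** The point holds as an internal inconsistency. For subjects who stop assessments before Day 28, 8.8 and footnote 15 prescribe different contact days, and nothing in the documents ranks one above the other. The consequence is confined to sites that follow 8.8 and to subjects who stop before Day 21 but remain alive and reachable. Their primary outcome is an earlier status carried forward, although a Day 21 call could have obtained it. Day 14 and Day 7 cure, second and fifth in the secondary testing order (SAP Section 6.4.2), are exposed in the same way.

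The number is unknown. The ceiling assumes that the 10% planning figure is right, that all of it falls in the exposed group, and that 77 per arm is the analysis denominator. The true number is likely smaller. The point still merits correction, because it concerns avoidable missing data on the primary endpoint and the remedy is already written in both documents.

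**What to change.** Amend the first paragraph of Protocol Section 8.8 to match footnote 15: subjects who stop assessments but still accept contact are called on each remaining key day, including Day 21, to assess Clinical Cure, survival and adverse events.

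Add a sentence to SAP Sections 6.1.5 and 6.4.1.1 stating that Clinical Cure status obtained at the Day 21 call is the Day 21 outcome, and that carry-forward applies only when no Day 21 contact was obtained. Apply the same rule at Day 7 and Day 14.

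The cost is a wording change to the protocol, a clarification in the SAP, and a few telephone calls that the schedule of assessments already requires. Sample size, endpoint and test are unchanged.
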